 - Any herpetic events confirmed due to talimogene laherparepvec (T-VEC) that require treatment with acyclovir or similar anti-viral agent.

Talimogene laherparepvec (T-VEC) treatment should be held if systemic acyclovir or other anti-viral is indicated. If ongoing anti-viral treatment is required, talimogene laherparepvec (T-VEC) treatment should be permanently discontinued.

 * Herpetic events due to wild-type HSV-1 or wild-type HSV-2 which require acyclovir and are not due to talimogene laherparepvec (T-VEC) (as confirmed by PCR testing) should not

be considered as DLTs caused by talimogene laherparepvec (T-VEC).

- 2. DLT will also be defined as any of the following talimogene laherparepvec (T-VEC)-related toxicity:
 - Grade 3 or greater immune-mediated AEs.
 - Grade 3 or greater allergic reactions.
 - Any grade plasmacytoma
 - Any other Grade 3 or greater hematologic or non-hematologic toxicity, with the exceptions of:
 - Any grade of alopecia,
 - Grade 3 arthralgia or myalgia,
 - Grade 3 fatigue, that improved to Grade 0-1 within 2 cycles,
 - Grade 3 fever,
 - Grade 3 diarrhea or vomiting responding to supportive care.

Dose Reductions/delay:

- Dose reductions with regards to changes in the concentrations of talimogene laherparepvec (T-VEC) are not permitted. However, patients may require a reduction in the volume injected due to a disease response (defined in dosing Section 7.1a) or due to local toxicity at the injection site.
- If talimogene laherparepvec (T-VEC) treatment was delayed due to AEs or other reasons by >1 week, that dose will be deemed to have been missed and the patient will proceed to the next scheduled treatment visit.
- If DLTs occur, talimogene laherparepvec (T-VEC) administration should be delayed until the DLT has resolved to at least CTCAE version 4.0 Grade
 1. (AEs less than DLT may also require talimogene laherparepvec (T-VEC) dose delay. See instructions in Table 2 below)
- If talimogene laherparepvec (T-VEC) dosing is delayed by more than 4 weeks (approximately 7 weeks from the previous dose) due to treatment related AEs, talimogene laherparepvec (T-VEC) should be permanently discontinued.
- If talimogene laherparepvec (T-VEC) dosing is delayed by more than 4 weeks (approximately 7 weeks from the previous dose) for reasons other than treatment-related toxicity, the case must be reviewed by the sponsor of the study (CTEP) to determine if the patient can resume talimogene laherparepvec (T-VEC) therapy.

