- If talimogene laherparepvec (T-VEC) has to be permanently discontinued for any reason other than a complete response, patient will be removed from further treatment with pembrolizumab (MK-3475) and will come off study.

Table 2: Treatment delays and discontinuation due to Specific AEsrelated to T-VEC				
Condition	Grade	Talimogene laherparepvec (T-VEC) modification		
Injection site reactions	Any grade	Volume of talimogene laherparepvec (T-VEC) injection may be adjusted and should be held based on the degree of local toxicities		
Active herpetic cutaneous or mucosal lesions, herpes labialis, or active dermatoses in the region of the injected tumors	Any grade	Mild: continue talimogene laherparepvec (T-VEC) lf requiring systemic acyclovir or similar anti-viral agents: Hold talimogene laherparepvec (T-VEC).		
• Serious herpetic events such as herpetic encephalitis, encephalomyelitis or disseminated herpetic infection	Any grade	Discontinue talimogene laherparepvec (T-VEC)		
 Any condition requiring corticosteroid dosing of >10 mg prednisone daily (or equivalent) and/or other immunosuppressive medication for related toxicities 	N/A	Hold talimogene laherparepvec (T- VEC) dosing until corticosteroid dose has decreased to <10 mg prednisone daily (or equivalent) and the other immunosuppressive medication has been stopped.		
Plasmacytoma	Any grade	Permanently discontinue talimogene laherparepvec (T-VEC)		
 Immune-mediated AEs (These may include pauci-immune glomerulonephritis, vasculitis, and pneumonitis, but may involve any organ system) 	Grade 2 or greater	Hold talimogene laherparepvec (T- VEC) (with the exception of vitiligo). If delay is > 12 weeks, discontinue talimogene laherparepvec (T-VEC)		
• Allergic reactions, or urticaria	Grade 2 or greater	Hold talimogene laherparepvec (T- VEC). If delay is > 12 weeks, permanently discontinue talimogene laherparepvec (T-VEC)		
Other talimogene laherparepvec (T-VEC) related grade 3+ AEs or intolerable grade 2 AEs (Except brief grade 3 fever, fatigue, pain, or nausea/vomiting responding to supportive care)		 Hold talimogene laherparepvec (T-VEC) until AE is grade 0-1. If delay is > 12 weeks, discontinue talimogene laherparepvec (T-VEC) If the AE was grade 4, decision to resume talimogene laherparepvec (T-VEC) upon recovery should be reviewed with the sponsor (CTEP) 		

c. Concomitant Medication/Supportive Care Guidelines for pembrolizumab (MK-3475).

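### Section 8.2b gives two conflicting limits, 4 weeks and 12 weeks, for stopping T-VEC after a treatment-related delay, and no text says which applies

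*Combined protocol and SAP*

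**What the plan says.** Section 8.2b sets time limits for a T-VEC delay in two places.

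- **The bullets under dose reductions and delay.** If T-VEC "dosing is delayed by more than 4 weeks (approximately 7 weeks from the previous dose) due to treatment related AEs", it should be permanently discontinued. A companion bullet sends a delay of the same length to CTEP for review when the reason is not treatment-related toxicity.
- **Table 2, on specific AEs related to T-VEC.** Two rows hold T-VEC and then state "If delay is > 12 weeks, discontinue talimogene laherparepvec (T-VEC". These are immune-mediated AEs of grade 2 or greater (vitiligo excepted), and other T-VEC-related AEs that are grade 3 or greater or intolerable grade 2. The row for allergic reactions or urticaria of grade 2 or greater states "If delay is > 12 weeks, permanently discontinue talimogene laherparepvec (T-VEC".

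The only pointer from the bullets to the table is a parenthesis: "AEs less than DLT may also require talimogene laherparepvec (T-VEC) dose delay".

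On the consequence, 8.2b says that if T-VEC is permanently stopped for any reason other than a complete response, the "patient will be removed from further treatment with pembrolizumab (MK-3475) and will come off study".

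Section 7.4d lists, among the criteria for removal from protocol treatment, a T-VEC delay of more than 12 weeks for any reason except a confirmed CR in the injectable lesions.

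**The concern.** The bullet covers treatment-related AEs without exception, so it reaches every event in the three Table 2 rows. Once a delay for one of these events passes 4 weeks, the bullet directs a permanent stop while the table still directs a hold. A site can follow either text and be in compliance with it.

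At stake is consistent treatment of the same clinical situation across sites. The limit decides more than T-VEC, because a permanent stop also takes pembrolizumab away. One site would end both drugs. Another would wait, restart T-VEC on recovery and keep the patient eligible for pembrolizumab.

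Such a delay could arise in ordinary care. The supportive-care text for pembrolizumab-related grade 2 pneumonitis starts the steroid taper after improvement to grade 1 and runs it for at least 4 weeks. Table 2 names pneumonitis among the immune-mediated AEs and holds T-VEC until the prednisone dose falls below 10 mg daily. T-VEC may restart before the taper ends, so a delay beyond 4 weeks is possible but not inevitable.

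**Working it through.** **Inputs.** T-VEC is given every 21 days, or 3 weeks (Section 7.1). The bullet's limit is 4 weeks, which it equates to about 7 weeks from the previous dose. The limit in the three Table 2 rows and in 7.4d is 12 weeks.

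**How delay is counted.** When a dose is more than 1 week late, "that dose will be deemed to have been missed and the patient will proceed to the next scheduled treatment visit". A delay of over 4 weeks must therefore be counted across missed doses, from the date on which the first held dose was due. On that basis, time from previous dose = 3 weeks + delay.

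- Bullet: 3 + 4 = 7 weeks. This reproduces the protocol's own figure.
- Table 2 rows, counted the same way: 3 + 12 = 15 weeks.
- Range in conflict: 12 − 4 = 8 weeks, or 8 / 3 ≈ 2.7 cycles.

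**The two rules side by side, for an event in one of the three rows:**

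| Delay due to the event | Weeks from previous dose | Bullet | Table 2 row |
|---|---|---|---|
| Up to 4 weeks | Up to 7 | Permanent stop not required | Hold, may resume |
| More than 4, up to 12 weeks | More than 7, up to 15 | Permanent stop | Hold, may resume |
| More than 12 weeks | More than 15 | Permanent stop | Stop |

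The rules disagree only in the middle line.

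**Can the texts be reconciled as they stand?**

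1. *Bullet for DLTs, table for lesser events.* The pointer to Table 2 hints at this. But the bullet is not limited to DLTs, and the three rows include grade 3 or greater immune-mediated, allergic and other events, most of which 8.2b defines as DLTs.
2. *Apply the stricter limit.* Stopping at 4 weeks leaves the three 12-week limits with nothing to do.
3. *Section 7.4d decides.* It agrees with 12 weeks. It can also be read as an outer limit that still operates for non-toxicity delays that CTEP has allowed to run past 4 weeks. It does not mention the bullet.
4. *Someone will be consulted.* CTEP review past 4 weeks is for delays not caused by treatment-related toxicity. Within the three rows, only one case goes to CTEP: "If the AE was grade 4, decision to resume talimogene laherparepvec (T-VEC) upon recovery should be reviewed with the sponsor (CTEP". Section 7.3 requires non-emergency steroid use to be discussed with the study chair. Neither provision names a time limit.

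**The corticosteroid row.** Table 2 also holds T-VEC for "Any condition requiring corticosteroid dosing of >10 mg prednisone daily (or equivalent" and for other immunosuppressive medication, until the dose has come down, with no time limit of its own. If the steroid is given for an event in one of the three rows, it is unclear whether the bullet's 4 weeks or that event's 12 weeks applies.

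**The case against.** The strongest reply is that a specific rule governs a general one. Table 2 is titled for specific AEs, and the bullet is a default for treatment-related AEs at large. On that reading both rules operate: the three rows keep 12 weeks, and the bullet still covers the rows without a limit, namely injection-site reactions, herpetic lesions held for antivirals, and steroid holds. Section 7.4d independently uses 12 weeks. The subsection is headed as guidelines and the bullet says should.

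Much of this stands. It is the most natural reading and makes 12 weeks the likely intent. It remains an inference, because the bullet carries no exception and no sentence gives the table precedence. The softer wording leaves a site with discretion but does not tell it which limit to use.

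A second reply is that the pembrolizumab consequence is narrower than it looks. For immune events also attributed to pembrolizumab, Table 1 in 8.2a already requires its permanent discontinuation for, among others, grade 3 or 4 pneumonitis, hepatic events, nephritis and myocarditis. In those cases the T-VEC limit does not decide whether pembrolizumab ends. That is correct and is carried into the conclusion.

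A reader might go further and infer that the 4-week rule costs confirmed responses. Section 10.3 documents best response while the patient is on protocol treatment, and the decision thresholds are small (2 responses in 17 for Cohort A, 5 in 25 for Cohort B). The documents do not support that step. They give no frequency for such delays. Section 10.3 does not say how a response confirmed after treatment stops would count. The study calendar in Section 9.0 has a pre-progression off-treatment column that appears to be marked for tumor measurements, so scanning does not appear to end with treatment. That table is poorly legible and its footnotes cannot be read, so the off-treatment scan rules cannot be established either way.

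**Conclusion.** The contradiction is real but limited. It concerns three rows of Table 2 and delays of more than 4 and up to 12 weeks, about 7 to 15 weeks from the previous dose. In that range the two texts give opposite instructions for T-VEC. They also differ on pembrolizumab, unless Table 1 has already required stopping it.

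The 7-week figure is the protocol's own. The 15-week figure assumes that Table 2 counts delay as the bullet does. That 12 weeks is the intended limit is an inference from 7.4d and from the specific nature of the table.

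No effect on ORR can be shown. The stated alpha and power (17.2% and 90.2% in Cohort A, 10% and 90% in Cohort B) and the sample sizes do not depend on this rule. The point should be corrected because sites need one stopping rule, not because the statistical design is at fault.

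**What to change.** Amend the bullet to read: *due to treatment related AEs, except for events for which Table 2 gives a 12-week limit*. Add one sentence stating that the 12-week limit also applies when T-VEC is held for steroids given for one of those events. Rows without a limit of their own then keep the 4-week default, and the text agrees with 7.4d. CTEP review after a grade 4 event in the other-AE row is untouched.

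If the clinical team intends 4 weeks, leave the bullet alone and change 12 to 4 in the three Table 2 cells.

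The cost is one clause and one sentence, or three table cells, by protocol amendment. Sample size, error rates and analysis do not change.

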7.3 Prohibited and Cautionary Concomitant Medications

Patients should not receive the following therapies during this trial:

- Antineoplastic systemic chemotherapy or biological therapy.
- Immunotherapy not specified in this protocol.
- Any non-study anti-cancer agent (investigational or non-investigational).
- Investigational agents other than pembrolizumab (MK-3475) and talimogene laherparepvec (T-VEC).
- Radiation therapy
 - Note: Administration of palliative radiation therapy to non-targeted lesions is allowed.
- Anti-viral agents, unless approved after consultation with the study chairs.
- Live vaccines: Examples of live vaccines include, but are not limited to, the following: measles, mumps, rubella, chicken pox, shingles, yellow fever, rabies, Bacillus Calmette-Guérin (BCG), and typhoid (oral) vaccine. Seasonal influenza vaccines for injection are generally killed virus vaccines and are allowed; however, intranasal influenza vaccines (e.g. Flu-Mist®) are live attenuated vaccines, and are not allowed.
- Systemic glucocorticoids for any purpose other than to modulate symptoms from an event of suspected immunologic etiology. The use of physiologic doses of corticosteroids may be approved after consultation with the Study Chairs.

Patients who, in the assessment by the investigator, require the use of any of the aforementioned treatments for clinical management should be removed from protocol treatment. Patients may receive other medications that the investigator deems to be medically necessary.

Any steroid use other than emergency situations must be discussed with the study chair.

- 7.4 Criteria for Removal from Protocol Treatment
 - a. Completion of protocol treatment (36 cycles)
 - b. Progression of disease or symptomatic deterioration (as defined in Section 10.2).
 - 1. A minority of subjects treated with immunotherapy may derive clinical benefit either delayed responses, stable disease, or increased overall survival despite initial evidence of progressive disease (PD).

Patients may be permitted to continue treatment beyond initial RECIST 1.1-defined PD as long as they meet the following criteria:

- Patients must be clinically stable with no change in performance status due to disease progression.
- No indication for immediate alternative treatment.

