	and the patient should be premedicated for the next scheduled dose. Patients who develop Grade 2 toxicity upon re-challenge, despite adequate premedication, must be permanently discontinued from protocol treatment. Stop Infusion. • Additional appropriate medical therapy may include but is not limited to: • IV fluids • Antihistamines • NSAIDS • Acetaminophen • Narcotics • Oxygen • Pressors • Corticosteroids • Epinephrine • Increase monitoring of vital signs as medically indicated until the patient is deemed medically stable in the opinion of the investigator. • Hospitalization may be indicated. • Patient is permanently discontinued from protocol

e. Concomitant Medication Considerations for talimogene laherparepvec (T-VEC)

Talimogene laherparepvec (T-VEC) is sensitive to acyclovir and other antiherpetic viral drugs and would be rendered ineffective. Thus, if systemic anti-herpetic medication is indicated, talimogene laherparepvec (T-VEC) must be discontinued.

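### When a systemic anti-herpetic drug is needed, Section 8.2e says to discontinue T-VEC but Section 8.2b and Table 2 say to hold it; one reading ends both study drugs

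*Combined protocol and SAP*

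**What the plan says.** Five places bear on a patient who needs a systemic anti-herpetic drug.

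- **Section 8.2e** (concomitant medication, T-VEC): "Thus, if systemic anti-herpetic medication is indicated, talimogene laherparepvec (T-VEC) must be discontinued". It gives no duration, no route to restart and no cross-reference.
- **Section 8.2b, item 1**: T-VEC "treatment should be held if systemic acyclovir or other anti-viral is indicated". The next sentence limits the permanent stop: "If ongoing anti-viral treatment is required, talimogene laherparepvec (T-VEC) treatment should be permanently discontinued".
- **Table 2 in Section 8.2b**, row for active herpetic lesions including herpes labialis, any grade. Mild cases continue T-VEC. For cases needing a systemic drug the entry reads "requiring systemic acyclovir or similar anti-viral agents: Hold talimogene laherparepvec (T-VEC". The next row, for encephalitis, encephalomyelitis or disseminated infection, says discontinue.
- **Section 8.2b, last dose-delay bullet**: "If talimogene laherparepvec (T-VEC) has to be permanently discontinued for any reason other than a complete response, patient will be removed from further treatment". The bullet goes on to name pembrolizumab as the treatment withdrawn and to take the patient off study.
- **Section 7.3** lists among prohibited treatments "Anti-viral agents, unless approved after consultation with the study chairs". Patients who need a prohibited treatment are to come off protocol treatment.

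**The concern.** Sections 8.2e and 8.2b item 1 give different actions for one trigger, and no text says which governs. Section 8.2e also has the stronger verb: must, against should in 8.2b.

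The two actions lead to different outcomes for the patient. A hold costs a T-VEC dose or so and lets pembrolizumab continue. A permanent stop ends both drugs. For a foreseeable and usually minor event such as a cold sore treated with a short acyclovir course, two sites following the same protocol could do opposite things.

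The primary endpoint is also within reach, because Section 10.3 has best response documented only while the patient is on protocol treatment. A patient removed early loses the chance of a later confirmed response.

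**Working it through.** **Step 1. One case under each rule.** Take a patient with herpes labialis who needs a short systemic antiviral course.

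| Source | Action on T-VEC | Pembrolizumab |
|---|---|---|
| 8.2b item 1 | Hold; permanent stop only if antiviral treatment is ongoing | Continues |
| Table 2, herpetic-lesion row | Hold | Continues |
| 8.2e, read as a pause | Same as hold | Continues |
| 8.2e, read as permanent | Ends | Ends; patient off study |
| 7.3, no study-chair approval | Ends | Ends; removed from protocol treatment |

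**Step 2. Is the permanent reading of 8.2e open?** The sentence does not say permanently, so the permanent stop is an interpretation. It is a reasonable one:

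- Table 2 uses hold and discontinue as different actions in adjacent herpetic rows.
- Table 2 uses discontinue, with no qualifier, for serious herpetic events, where a pause is not a natural meaning.
- For the same delay of more than 12 weeks, Table 2 says discontinue for immune-mediated events and permanently discontinue for allergic reactions. Omitting the adverb therefore does not signal a temporary stop.

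**Step 3. Which rule fits the rest of the protocol?** The hold.

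- Section 8.2b counts as a DLT "Any herpetic events confirmed due to talimogene laherparepvec (T-VEC) that require treatment with acyclovir or similar anti-viral agent", and the instruction for a DLT is a delay: "If DLTs occur, talimogene laherparepvec (T-VEC) administration should be delayed until the DLT has resolved". Under the strict reading of 8.2e the same event ends treatment.
- Herpetic events shown to be wild-type HSV are not T-VEC DLTs even when they need acyclovir. The strict reading would still end both drugs.
- Section 3.2f.3 asks for risks and benefits to be weighed before acyclovir is given. An automatic permanent stop does not fit that.
- The reason given in 8.2e, that the antiviral makes T-VEC ineffective, explains stopping while the drug is given and no longer.

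**Step 4. Cost of a hold.** A cycle is 21 days, so any 21 consecutive days contain exactly one scheduled Day 1. If T-VEC is held only during the course, a course of up to 21 days touches at most one of 36 planned injections.

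**Step 5. How often the trigger might occur.** Inputs: 17 + 25 = 42 eligible patients (Sections 11.1 and 11.2); oral or corneal herpes in 5.5% of T-VEC patients (Section 3.2e.2); design response rates of 25% (Cohort A) and 30% (Cohort B). The share of cases needing a systemic drug is not given. I assume 25% to 100%, with response independent of herpes.

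- Expected patients, all cases systemic: 42 × 0.055 = 2.31.
- Expected patients, 25% systemic: 2.31 × 0.25 = 0.58.
- Chance of at least one, all systemic: 1 − 0.945^42 = 0.907.
- Chance of at least one, 25% systemic: 1 − (1 − 0.01375)^42 = 0.441, where 0.055 × 0.25 = 0.01375.
- Would-be responders, Cohort A: 17 × 0.055 × 0.25 = 0.234; at the 25% share, 0.058.
- Would-be responders, Cohort B: 25 × 0.055 × 0.30 = 0.413; at the 25% share, 0.103.

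These figures lean high. Sections 5.3j and 5.3k exclude patients who need intermittent systemic anti-herpetic treatment, some responses will already be confirmed, and some sites will hold.

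**The case against.** The best defence is that the texts can be reconciled. The off-study bullet applies only to a permanent T-VEC stop. On this trigger 8.2b separates holding from permanent discontinuation, and 8.2e omits the adverb. Its stated rationale supports only a temporary stop. The dose-modification section and its table are specific and clear, and they are where a site managing a herpetic lesion would look. Section 7.3 brings in the study chairs, who can settle the matter, and an antiviral they approve is outside the prohibition. The comparison of the 12-week rows is also weaker than it looks, because Section 7.4d makes such a delay final anyway.

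Much of this stands. The permanent stop is not stated in 8.2e, the chair consultation lowers the risk, and 7.3 does not force removal once approval is given. It does not remove the conflict. The contrast between hold and discontinue in the two herpetic rows remains, Section 7.3 does not tell the chairs which rule applies, and a site should not have to infer that a sentence saying must yields to one saying should.

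The size is also fairly challenged. The 44% to 91% range is the chance that some patient meets the trigger. It is not the chance that anyone is wrongly removed, which the documents give no basis to compute. The 100% share is an extreme, since Table 2 expects mild cases that continue T-VEC.

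**Conclusion.** The point holds. The protocol gives conflicting dosing instructions for one foreseeable event, and 8.2e is the outlier. The practical range runs from at most one missed T-VEC injection, for a course of up to 21 days, to the end of both study drugs. The outcome depends on how a site reads 8.2e and on what the study chairs advise.

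On the assumed 25% to 100% share, about 0.6 to 2.3 of 42 patients would meet the trigger, with 0.06 to 0.23 would-be responders among them in Cohort A and 0.10 to 0.41 in Cohort B. An effect on a cohort decision is possible but unlikely. The reason to act is the contradictory instruction and the needless loss of treatment it allows. It should be fixed.

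**What to change.** Keep the 8.2b rule and reword the sentence in 8.2e along these lines: *T-VEC must be held while systemic anti-herpetic medication is given, and permanently discontinued if ongoing treatment is required or for a serious herpetic event (see 8.2b and Table 2).*

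As a smaller clarification, add to the antiviral item in 7.3: *A time-limited systemic course approved by the study chairs and managed under 8.2b does not by itself require removal from protocol treatment.* This largely restates the existing approval route, but it ties that route to the hold rule.

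The cost is one reworded sentence and one added sentence. No new procedures, data or patients are needed.
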